13.1 Adverse events

All recorded adverse events will be coded according to the Medical Dictionary for Regulatory Activities (MedDRA). Treatment emergent adverse event (TEAE) is defined as an AE that begins or worsens in severity after at least one dose of study drug has been administered. Non-treatment emergent AEs are listed only.

TEAEs will be summarized using frequency and subject based tables. TEAEs will be tabulated by treatment group, system organ class (SOC), preferred term (PT), causality and severity. For analysis purposes, each subject will also be categorized by the maximum severity reported for a given TEAE and these will be tabulated by maximum severity. TEAEs will be summarized separately for treatment period (D1-D5) and short-term follow-up period (D6-D30). TEAEs are not collected, and therefore not reported, during the mid-term follow-up.

Serious adverse events (SAEs) and AEs leading to discontinuation will be summarized by treatment groups. All deaths up to D90 are reported as SAEs.

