8.4 Evaluation of safety

All patients who receive a minimum of one administration of study medication are included in the safety analysis.

Adverse Events

Treatment Emergent Adverse Effects (TEAEs) and SAEs are classified according to the Medical Dictionary for Regulatory Activities (MedDRA) SOC and the preferred term. The incidence of these events will be summarised by treatment group in tables which will also include information on severity and relationship to study medication. These summaries will be based on the Safety Set. The frequency of complications is summarised by treatment groups in terms of counts.

Vital Signs

Vital signs data (BP, HR and temperature) is summarised by treatment group separately at D0, D1, D2, D3, D4, D5, D6, D9, D13 and D30. The maximum change from baseline over the 30-day follow-up period will be calculated for each patient and summarised.

Vital signs summaries will be in terms of mean, median, standard deviation (SD), minimum and maximum.

Clinical Laboratory Parameters

Descriptive statistics (mean, median, SD, minimum and maximum) for biochemistry and haematology will be obtained and tabulated by treatment group at D0, D1, D2, D3, D4, D5, D6 and D30. Descriptive statistics (mean, median, SD, minimum and maximum).

Shift tables (within, below and above the normal range) will also be provided for each parameter in relation to the maximum change from baseline from D0 over the complete 30-day follow-up period.

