- Length of hospital stay, in terms of hospital free days at D90
- Length of stay at another health care facility at D90
- Length of haemodialysis needed

6 Sample size considerations

The primary efficacy endpoint is all cause mortality at D30. Death within 36 hours from the first dose of the study treatment leads to exclusion from efficacy analysis. A sample size of 129 eligible patients for the primary efficacy analysis, with a 2:1 ratio to active (86) and placebo (43), will detect the difference of 22% between the two treatment groups with 80 % power using 2-sided z-test with 0.05 significance level. To take account of the planned interim analysis, calculations assume that 2 sequential tests are made (in addition to final analysis) and the O'Brien-Fleming spending function is used to determine the test boundaries. Statistical analysis plan for the interim analyses will be presented in a separate document.

Power calculation assumes 37 % proportion of events on placebo group and 15 % proportion for the active treatment group.

To achieve a sample size of 129 for the primary efficacy analysis, taking account the estimated amount of early deaths within 36 hours from first dose of the study treatment (estimated 15 %), there should be 152 patients randomised to the study.

Study was discontinued after the first Interim analysis. Therefore, the sample size did not reach the 129 patients aimed for.

7 Statistical hypotheses

The primary objective of this study is to evaluate the safety and the efficacy of FP-1201-lyo over placebo on reducing all-cause mortality at study day 30, i.e., the null-hypothesis to be tested is

H_0 : FP-1201-lyo is not superior to control with respect to all-cause mortality at study day 30

against

H_1 : FP-1201-lyo is superior to control with respect to all-cause mortality at study day 30

8 Analysis datasets

Statistical analyses will be performed on the following analysis datasets.

The Full Analysis Set for Efficacy (FAS-E) consists of all randomised patients receiving study treatment but excluding the early deaths (within 36 hours from first dose of study treatment) and comprises the analysis set on which the primary efficacy analysis is based.

The Per Protocol Set (PPS) consists of the patients in the FAS-E excluding patients with major protocol violations possibly affecting the primary study endpoint analysis.

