The precise definition of the PPS at the patient level was planned to be identified at the blind review conducted both before the second interim and final analysis. The detailed criteria for patient classification will be prepared before database lock. Subject classification was to be created first for the subjects included in the second interim analysis, and later amended for the final analysis with the subjects that were not included in the interim analysis.

The first Interim analysis (after 35 evaluable patients) was based on FAS-E dataset. No classification for PPS was done for the first Interim analysis.

Statistical analyses for efficacy, PD, tentative disease specific markers and pharmacoeconomic variables are performed on both the FAS-E and PPS.

Study was discontinued after the first interim analysis. Subject classification document defining the analysis datasets in detail will be prepared and signed before database lock.

The Full Analysis Set for Safety (FAS-S) consists of all randomised patients receiving study treatment and comprises the analysis set on which the evaluation of safety is based. All safety analyses are performed on the FAS-S analysis dataset.

9 General statistical considerations

Summary statistics will include at least the number of subjects, mean, standard deviation, median, minimum and maximum for continuous variables, and frequencies and percentages for categorical variables. All data collected will be listed by subject.

In the statistical analyses a p-value less than 0.05 will be considered as an indication of statistical significance. If not stated otherwise, all tests will be performed as two-sided tests and two-sided 95% confidence intervals will be produced. Missing values will not be imputed in the analyses.

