12.3.2 Pharmacoeconomic analysis

Following pharmacoeconomic endpoints were defined for the study:

- Length of ICU stay, in terms of ICU free days at D90
- Length of hospital stay, in terms of hospital free days at D90
- Length of stay at another health care facility at D90
- Length of hemodialysis needed (at D90)

Due to early discontinuation of the study, these endpoints will not be analysed.

13 Analysis of safety and tolerability

All subjects in the SAF-S analysis set (all randomised patients receiving study treatment) will be included in the safety and tolerability analysis. Safety variables to be analysed are; adverse events, clinical laboratory parameters, vital signs and physical examination.

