Table 14.2.1.11.3	Length of stay in another health care facility up to D30 excluding deaths (FAS-E)
Table 14.2.1.11.4	Length of stay in another health care facility up to D30 excluding deaths (PPS)
Table 14.2.1.12.1	IAP values by timepoint (FAS-E)
Table 14.2.1.12.2	IAP values by timepoint (PPS)
Table 14.2.1.12.3	IAP values by timepoint excluding early deaths (FAS-E)
Table 14.2.1.12.4	IAP values by timepoint excluding early deaths (PPS)
Table 14.2.1.13.1	IAP grades by timepoint (FAS-E)
Table 14.2.1.13.2	IAP grades by timepoint (PPS)
Table 14.2.1.13.3	IAP grades by timepoint excluding early deaths (FAS-E)
Table 14.2.1.13.4	IAP grades by timepoint excluding early deaths (PPS)
Table 14.2.1.14.1	Disability on D90 measured with mRS (FAS-E)
Table 14.2.1.14.2	Disability on D90 measured with mRS (PPS)
Table 14.2.1.14.1	Neutralizing antibodies (FAS-E)
Table 14.2.1.14.2	Neutralizing antibodies (PPS)
	Pharmacodynamics
Table 14.2.2.1.1	MxA concentration (FAS-E)
Table 14.2.2.1.2	MxA concentration (PPS)
Table 14.2.2.2.1	MxA ANOVA (FAS-E)
Table 14.2.2.2.2	MxA ANOVA (PPS)
Table 14.2.2.3.1	CD73 concentration (FAS-E)
Table 14.2.2.3.2	CD73 concentration (PPS)
Table 14.2.2.4.1	CD73 ANOVA (FAS-E)
Table 14.2.2.4.2	CD73 ANOVA (PPS)
Table 14.2.2.5.1	Potential inflammatory markers (FAS-E)
Table 14.2.2.5.2	Potential inflammatory markers (PPS)
Table 14.2.2.6.1	PIM ANOVA (FAS-E)
Table 14.2.2.6.2	PIM ANOVA (PPS)
	Subgroup analyses
Table 14.2.1.1.1	All-cause mortality D30 by subgroups
Table 14.2.1.2.1	Logistic regression of All-cause mortality D30 by subgroups
	Safety Tables
Table 14.3.1	Extent of exposure and compliance (FAS-S)
Table 14.3.2	Summary of TEAEs (FAS-S)
Table 14.3.3.1	Treatment emergent adverse events (FAS-S)
Table 14.3.3.2	TEAEs by causality (FAS-S)
Table 14.3.3.3	TEAEs by severity (FAS-S)
Table 14.3.3.4	TEAEs by maximum severity (FAS-S)
Table 14.3.3.5	TEAEs by causality and severity (FAS-S)
Table 14.3.3.6	TEAEs by causality and maximum severity (FAS-S)
Table 14.3.4.1	TEAEs during treatment period (FAS-S)
Table 14.3.4.2	TEAEs during treatment period by causality (FAS-S)
Table 14.3.4.3	TEAEs during treatment period by severity (FAS-S)

Table 14.3.4.4	TEAEs during treatment period by maximum severity (FAS-S)
Table 14.3.4.5	TEAEs during treatment period by causality and severity (FAS-S)
Table 14.3.4.6	TEAEs during treatment period by causality and maximum severity (FAS-S)
Table 14.3.5.1	TEAEs during short-term follow-up period (FAS-S)

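### The D6–D30 TEAE tables name only the all-treated safety set as their base, so a difference in mortality alone can shift crude percentages of non-fatal TEAEs

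*SAP*

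**What the plan says.** SAP 13.1 gives the form of the summary, "TEAEs will be summarized using frequency and subject based tables", and the split by period: "TEAEs will be summarized separately for treatment period (D1-D5) and short-term follow-up period (D6-D30". It gives no denominator for either period.

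The base has to be read from other places:

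- SAP 8: "All safety analyses are performed on the FAS-S analysis dataset".
- SAP 13, opening paragraph: "All subjects in the SAF-S analysis set (all randomised patients receiving study treatment) will be included in the safety and tolerability analysis". (SAF-S is evidently FAS-S.)
- SAP 19.3: the first D6–D30 table is titled "TEAEs during short-term follow-up period (FAS-S", and the five that follow carry the same label.
- SAP 9: the general rule for summaries is "frequencies and percentages for categorical variables".
- Protocol 8.4: "The incidence of these events will be summarised by treatment group".

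Neither document defines a set at risk at D6, a rate per unit of follow-up, or a way of handling death in the TEAE summaries. SAP 11 describes exposure and study duration by arm but does not link them to adverse events.

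**The concern.** A patient who dies before D6 cannot contribute a D6–D30 event but stays in the FAS-S count. FAS-S also keeps the early deaths within 36 hours, put at 15% in SAP 6, which FAS-E removes. Patients who die after D6 are observed for only part of the window. Death by D30 is the primary endpoint, so the quantity the drug is meant to change also sets how many patients can have a late TEAE and for how long.

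Elsewhere the SAP allows for this. SAP 12.2 analyses dialysis days, hospital days and intra-abdominal pressure both with and without patients who died, and scales organ-failure-free days to the days that have a SOFA score. TEAEs get no equivalent. What is at stake is whether a reader of the D6–D30 tables can tell a toxicity difference from a survival difference.

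**Working it through.** **Inputs from the documents (SAP 6).** "Power calculation assumes 37 % proportion of events on placebo group and 15 % proportion for the active treatment group"; these are D30 deaths among patients who survive 36 hours. Early deaths are 15%, allocation is 2:1, and 129 are evaluable (86 and 43).

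**Assumptions, not in the documents.** Early deaths are 15% in both arms. A share s of the later deaths falls before D6, with s = 25–75%. The non-fatal TEAE risk is the same in both arms.

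**The plan's own figure.** The documents give no expected TEAE percentage, so the check is that the mortality inputs are the operative ones. A fixed-sample calculation for 37% v 15% at 2:1 gives 132 in total against the stated 129; power with 43 on placebo is 0.792. A group-sequential simulation with looks at 35, 84 and 129 gives power 0.803, and 0.396 by the second look (protocol 8.6: about 40%). 129 / 0.85 = 151.8, so 152 randomised. The inputs reproduce the plan.

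**Step 1: alive at D6.** With m the later D30 mortality, P(alive at D6) = 0.85 × (1 − s·m). At s = 50%:

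- active: 0.85 × (1 − 0.075) = 78.6%, so 21% dead
- placebo: 0.85 × (1 − 0.185) = 69.3%, so 31% dead

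Over s = 25–75%, 18–25% of active and 23–39% of placebo are dead by D6.

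**Step 2: fixed risk r among those alive at D6.** The spurious difference on the FAS-S base is 0.85 × r × s × (0.37 − 0.15) = 0.187·r·s. At s = 50%, r = 60% this is 5.6 points (47.2% active v 41.6% placebo). Over s = 25–75% and r = 40–80% it runs from 0.187 × 0.40 × 0.25 = 1.9 to 0.187 × 0.80 × 0.75 = 11.2 points (ratio 1.06–1.23).

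**Step 3: constant daily risk h while alive.** Deaths after D6 are spread evenly over 25 days. A survivor has an event with probability 1 − exp(−25h); a patient dying in the window with probability 1 − [1 − exp(−25h)]/(25h). Patient-days per treated patient at s = 50%:

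- active: 25 × 0.7225 + 12.5 × 0.06375 = 18.86
- placebo: 25 × 0.5355 + 12.5 × 0.15725 = 15.35
- ratio 1.23 (1.18–1.29 over s = 25–75%)

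The last column below counts every D6–D30 death as a TEAE as well. That is an upper bound, since some fatal events begin before D6.

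| s | h | Non-fatal TEAE, active v placebo | Difference | Any TEAE including deaths, difference |
|---|---|---|---|---|
| 25% | 0.02 | 30.5% v 26.1% | +4.4 | −6.7 |
| 25% | 0.05 | 55.7% v 48.3% | +7.3 | −0.7 |
| 50% | 0.02 | 29.8% v 24.4% | +5.4 | −2.0 |
| 50% | 0.05 | 54.3% v 45.0% | +9.3 | +4.0 |
| 75% | 0.02 | 29.1% v 22.7% | +6.4 | +2.7 |
| 75% | 0.05 | 52.9% v 41.6% | +11.3 | +8.7 |

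Three of the six any-TEAE rows reverse. The first is 38.0% active v 44.7% placebo.

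**Step 4: a smaller mortality difference.** With an illustrative 25% v 30%, the Step 3 model gives +1.0 to +2.6 points for non-fatal TEAEs. With equal mortality and timing it gives zero.

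**Step 5: does the denominator alone repair it?** Not fully. At s = 50%, h = 0.05, dividing by patients alive at D6 gives 54.3/78.6 = 69.0% active v 45.0/69.3 = 64.9% placebo. Deaths inside the window still shorten follow-up. Events per patient-day at risk are equal in this model.

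**Step 6: scale.** SAP 2 reports 35 evaluable patients at the interim. If 2:1 held, about 35/3 ≈ 12 were on placebo, and one patient is 1/12 ≈ 8 points. The treated number per arm is not given.

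**The case against.** A reader might infer that the arm with fewer deaths will look worse throughout the safety tables, and that a drug that raises mortality will look safer. The documents do not support that. Protocol 6.3.1.2 reports adverse events leading to death by D30 as SAEs, and SAP 13.1 reports all deaths to D90 as SAEs, so extra deaths enter the serious and fatal rows against the arm that has them. The last column of the table shows the any-TEAE row going either way. This objection stands and limits the point to non-fatal TEAEs. It does not rescue the tables, because an any-TEAE row then mixes two opposing effects of mortality.

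Other objections and what remains of them:

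- **The denominator is inferred.** This is correct. An analysis-set label is not a stated denominator, and no table shells are given. But FAS-S is the only base named, and leaving the denominator unstated needs the same sentence in the SAP.
- **The size rests on the hoped-for mortality effect.** This is also correct, and Step 4 shows how quickly it shrinks.
- **The summaries are descriptive.** No test or interval between arms is planned for TEAEs, and SAP 19.4 lists deaths and TEAEs by patient. This lowers the stakes, but readers will still set the two percentages side by side.
- **Survivors may be under-observed.** Under the key to protocol Table 6, assessments before D30 stop once a patient leaves the operating hospital. Event capture may then fall while days alive accrue, which would bias a rate per day alive the other way. The size cannot be derived. The time base should therefore be time alive and under observation.

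**Conclusion.** The point holds for non-fatal TEAEs. The only base named for the D6–D30 tables includes patients who could not have an event in that window, and no at-risk alternative is planned. The spurious excess in the arm with fewer deaths is about 2–11 points at the planned 15% v 37%, about 1–3 points at 25% v 30%, and zero with equal mortality and timing. These figures rest on assumed death timing (25–75% of later deaths before D6), assumed event rates equal in the two arms, and equal early deaths. At the size the trial reached, the effect is roughly one placebo patient. No general direction can be claimed for any-TEAE, serious or fatal rows. This is a cheap improvement to the safety reporting; the primary analysis is not affected.

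**What to change.** In SAP 13.1:

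1. State the denominator for tables 14.3.5.1–14.3.5.6 as patients alive and under observation at the start of D6, and print that number for each arm.
2. For the overall, by-period and serious TEAE summaries, add events per 100 patient-days alive and under observation.
3. Show fatal and non-fatal TEAEs separately.
4. Keep the crude FAS-S counts alongside.

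The cost is SAP wording and extra table columns. Dates of death (protocol 6.2.1) and dates and times of event onset (protocol 6.3.1.4) are already recorded, and SAP 8 places database lock still ahead. The end of observation for transferred or discharged patients has to be defined. The rates, and any confidence intervals given with them, will be imprecise at this sample size and should be labelled descriptive.

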7 STUDY CONDUCT

For the purposes of this study, study day 0 (D0) is defined as the day of surgery and the first day of treatment with FP-1201-lyo or placebo. All days thereafter are defined as “Dn”, denoting the number of postoperative days (e.g. D1, D2 etc.) until D30. A follow-up assessment regarding the final outcome at D90 (3 months) is carried out using patient files or phone. For NAb assessment on D30 patient is invited for a laboratory visit (D30 ± 5 days).

Baseline assessments consist of those carried out in the screening period and those prior to the first dose of study medication on D0.

The study consists of the following study periods and tests and evaluation time points:

- **Baseline period:** Screening and study day 0 (D0) pre-dose
- **Treatment period:** D0 0 hrs to D5 (i.e., D0, D1, D2, D3, D4, and D5)
- **Short term follow-up period:** D6 to D30 daily if patient still hospitalized
- **Mid-term (final) follow-up:** D90 (3 months) through patient charts and registers and by phone.

For patients whose conditions have improved to the point where they are discharged from the ICU and the Investigator decides not to continue study treatment, the study assessments schedule should be followed. If an improving patient is discharged from the ICU during the treatment period then the patient will be followed daily during hospitalisation (in the operating hospital), and after a possible hospital discharge at D30.

A schedule for the tests and evaluations to be conducted in this study is found in the flow charts. Details on the timing of each assessment on a given study day is given in the flow charts.

The expected duration of the study for each patient is 1 month plus a patient records based follow up at 3 months.

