- Blood pregnancy test if relevant (only for females under age of 60 years)
- Haematology (refer to Section 6.3.2 for specific haematology variables)
- Pharmacodynamics (PD): MxA sample for central testing within 1 hr pre-dose
- Secondary efficacy: Neutralizing antibodies IFN-beta (NABs) sample within 1 hr pre-dose
- Tentative Disease Specific Marker CD73 and Potential Inflammatory Marker (PIM) samples for central testing within 1 hr pre-dose

- Recording of concomitant medications and therapies
- Collection of Adverse Events from this time point onward: All Adverse Events and Serious Adverse Events will be collected from the time of informed consent signature and throughout the study until the last follow-up visit.
- Recording of major surgical outcomes affecting patient
 - open abdomen (yes/no)
 - left renal vein ligated (yes/no)
 - Clamping time above the renal arteries

In practice, at arrival at the ICU standard artery-astrup analysis for haematology and biochemistry are performed. Tubes for disease and medication specific markers are drawn at the same time and stored in the ICU. After sampling, the study medication is begun. The study medication is also stored in the ICU.

7.5 TREATMENT PERIOD (D0 to D5) and SHORT TERM follow-up period (D6 to D30): STUDY MEDICATION ADMINISTRATION, PATIENT CARE, AND ASSESSMENTS

The study treatment period comprises D0 to D5 inclusive. Most procedures and assessments to be performed on D0 are pre-dose (with the exception of recording of SOFA scoring, concomitant medications and therapies and AE reporting) and they are detailed in Section 7.4.2.2.

The procedures and assessments to be performed on D0 from the time of study medication administration to D5 are detailed in Section 7.5.1.

The procedures and assessments to be performed in the short-term follow-up period are detailed in Section 7.5.2.

Assessments from D0 and prior to D30 are only performed if the patient is hospitalised in the operating hospital (where the patient was operated and recruited in the trial).

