- + Study specific procedures must be performed after informed consent for the study is obtained. If ICU standard procedures are in line with the study procedures and if the timing of RAAA diagnosis, consent, operative treatment and dosing preclude repetition of procedures for the purposes of the study, then standard patient care test results may be used for screening even prior to obtaining consent
- ∇ Study medication, FP-1201-lyo or placebo is administered as a bolus intravenous injection, followed by a 5 ml flush of sterile saline. On D0 the first dose of study medication is administered at 0h. Subsequent doses from D1 to D5 are administered every 24 hours ± 1 hour.
- ❖ SOFA scores are assessed daily in the ICU from D1 to D30, as applicable by standard clinical treatment at that point (therefore if a patient doesn't have an arterial line, no arterial blood sampling should be taken)

Flow Chart for the Short Term and Mid Term Follow-up Periods

ASSESSMENTS	Short Term Follow-Up*				
	D6	D9**	D13**	D30	D90 (+14 days) 3 months
Check whether patient is in the ICU	X	X	X	X	
Check whether patient is on ventilation	X	X	X	X	
Check whether patient is on organ support (hemodialysis)	X	X	X	X	X
SOFA Scoring ❖ (worst daily value should be used)	X	X	X	X	
Ventilator Free Days (VFDs)	X	X	X	X	
Physical Examination	X	X	X	X	
Vital Signs; Temp, BP, HR (closest to 8am)	X 6-10am	X 6-10am	X 6-10am	X 6-10am	
Blood Biochemistry	X 6-10am	X 6-10am	X 6-10am	X 6-10am	
Haematology	X 6-10am	X 6-10am	X 6-10am	X 6-10am	
Intra-abdominal pressure (IAP)	X 6-10am	X 6-10am	X 6-10am		
MxA, CD73 and PIM	X 22h±2h since Dose 6	X 6-10am	X 6-10am		
NAbs				X D30±5D	
Mortality (reason/diagnosis of death)				X	X
Concomitant Medications/Therapies	←-----X-----→				
AE Recording	←-----X-----→				
Deaths Recording			X		X
mRS					X

KEY:

- * Assessments prior to D30 are only performed if patient is still hospitalised in the same hospital initially operated. If the patient is moved to a different hospital, assessments will not be done. If study treatment is terminated early by Investigator decision due to patient improvement, the study assessment schedule should be followed as normal.

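### SAP 13.1 gives the treatment period for the by-period TEAE tables as D1–D5, against D0–D5 elsewhere; read literally, events starting on D0 after Dose 1 fall in neither period

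*SAP*

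**What the plan says.** SAP 13.1 defines a TEAE as "an AE that begins or worsens in severity after at least one dose of study drug has been administered". The same paragraph then sets the reporting split: "TEAEs will be summarized separately for treatment period (D1-D5) and short-term follow-up period (D6-D30".

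The other definitions of the treatment period start a day earlier:

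- Protocol section 7 lists it as "D0 0 hrs to D5 (i.e., D0, D1, D2, D3, D4, and D5".
- Protocol section 7.5 states: "The study treatment period comprises D0 to D5 inclusive".
- The key to the flow chart in SAP 19.2 states: "On D0 the first dose of study medication is administered at 0h". The chart has a D0 column with Dose 1 under the treatment-period heading, and adverse event recording is marked in that column.
- The SOFA schedule in SAP 19.2 also lists D0 post-dose under the treatment period.

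The table plan in SAP 19.3 has six treatment-period tables (14.3.4.1–14.3.4.6), the first titled "TEAEs during treatment period (FAS-S", and six follow-up tables (14.3.5.1–14.3.5.6). The titles carry no day range, and no separate set is planned for D0.

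Protocol 8.4 does not ask for a split by period. It says "The incidence of these events will be summarised by treatment group in tables", with severity and relationship to study medication.

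**The concern.** Under the SAP's own definition, an adverse event that begins on D0 after Dose 1 is treatment-emergent. Under the windows in the same section, it belongs to neither period. A reader of a table of TEAEs during the treatment period would expect it to include reactions to the first injection. If 13.1 is followed to the letter, those with onset on D0 would be absent, without notice, from the main treatment-period table and from its causality and severity versions.

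The uncovered time is not arbitrary. Protocol 5.8 names fever, tachycardia and rigor as anticipated effects and says that they tend to follow soon after dosing. SAP section 15, which lists the departures from the protocol's planned analyses, does not mention a shorter treatment period, so nothing there would alert the reader.

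**Working it through.** The documents state no figure to reproduce. The check sets the windows against the days on which a TEAE can start.

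**Inputs**

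- Days on which a TEAE can start: D0 (after Dose 1) to D30. The start follows from SAP 13.1 and the flow-chart key in SAP 19.2; the end is in protocol 6.3.1.2. That gives 31 study days, the first of them partial.
- Dosing days: D0 to D5, so 6 (protocol synopsis; SAP 19.2).
- Windows in SAP 13.1: D1–D5 (5 days) and D6–D30 (25 days).
- Treatment period in protocol 7 and 7.5: D0–D5 (6 days).

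**Coverage**

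| Treatment window | Days in window | Dosing days covered | Days in both windows together | D0–D30 days in neither |
|---|---|---|---|---|
| D1–D5 (SAP 13.1) | 5 | 5 of 6 | 5 + 25 = 30 | 31 − 30 = 1 (D0) |
| D0–D5 (protocol) | 6 | 6 of 6 | 6 + 25 = 31 | 31 − 31 = 0 |

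**Could day numbering explain D1–D5?** If D1 meant the first dosing day, six daily doses would run D1–D6 and follow-up could not start on D6. SAP 13.2 also labels D0 as baseline, and the SAP flow chart puts Dose 1 on D0 and Dose 6 on D5. The numbering in 13.1 is therefore the usual one, and its treatment window omits D0.

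**Tables affected (SAP 19.3)**

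- All TEAE tables: 14.3.2 (1) + 14.3.3.1–14.3.3.6 (6) + 14.3.4.1–14.3.4.6 (6) + 14.3.5.1–14.3.5.6 (6) + 14.3.7 (1) + 14.3.8 (1) = 21.
- Would omit D0-onset events under literal programming: 14.3.4.1–14.3.4.6 = 6.
- Not split by period: 1 + 6 + 1 + 1 = 9, with 14.3.7 and 14.3.8 holding only the events that qualify for them.
- Cover D6–D30, unaffected by the D0 question: 6.
- Check: 6 + 9 + 6 = 21.

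The documents contain no data on event timing, so no share or number of omitted events can be given.

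**The case against.** The strongest reply is that the documents do place D0 after dosing in the treatment period. The protocol says so twice, the SAP flow chart shows it, and the table titles carry no day range. Only one parenthesis disagrees. It is probably a drafting slip, and a programmer might well resolve it in favour of the protocol. This stands, and it makes the consequence conditional: events are omitted only if the parenthesis is followed over everything else. A reader might infer that D0 events are left unassigned throughout the documents; they are not.

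The reply also holds on scale. The by-period tables are descriptive and were added by the SAP. Reactions to Doses 2–6, given on D1–D5, are captured even under the literal wording. Protocol 6.3.1.3 allows some common ICU signs to go unrecorded as adverse events. The study stopped after an interim analysis of 35 evaluable patients, so the number of events affected may be small or zero.

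The reply does not remove the contradiction. SAP 13.1 is the section that specifies these tables, and its day range is a stated analysis rule that gives the wrong content if applied.

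A reader might also infer that 13.1 is at fault over adverse events that begin before Dose 1 and become TEAEs by worsening, since "All Adverse Events and Serious Adverse Events will be collected from the time of informed consent signature". That is missing detail, not a contradiction. Time of worsening is not among the items listed in protocol 6.3.1.4, and a default to the treatment period could misplace events that worsened on D6–D30. No rule for such events is proposed here.

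**Conclusion.** The point holds as an internal contradiction with a limited consequence. D1–D5 in SAP 13.1 conflicts with the D0–D5 treatment period in protocol 7 and 7.5 and with the SAP's own flow chart. On the assumption that 13.1 is programmed as written, the gap is at most one study day, D0 after Dose 1. Six of the 21 TEAE tables would undercount first-dose events, and the two period sets would not cover all TEAEs in the overall tables.

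A reader might infer that first-dose reactions would be lost from the safety analysis. The documents do not support that. TEAEs starting on D0 stay in Tables 14.3.2 and 14.3.3.1–14.3.3.6, which include causality, severity and maximum severity, in 14.3.7 and 14.3.8 where they qualify, and in Listing 16.2.26. No endpoint, hypothesis test or analysis set is affected. The correction is still worth making, because the omission would be silent and would fall on the first exposure to study drug.

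**What to change.** In SAP 13.1, define the treatment period for the by-period TEAE summaries as running from the first dose on D0 to D5, and keep short-term follow-up as D6–D30. State that TEAEs are assigned to a period by their recorded onset date and time.

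The cost is a revised sentence in the SAP and the matching programming. Protocol 6.3.1.4 already requires onset date and time, so no new data are needed. SAP section 8 places database lock in the future, so the change can be made before it. It restores a definition already fixed in the protocol and does not depend on the trial's results.
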